## **7.0 Study Procedures**

All study procedures are being conducted for research purposes only.

**Height** – A stadiometer will be used to collect standing height. Participants will be asked to remove their shoes prior to the assessment. Height will be obtained to the nearest cm.

**Bioelectrical Impedance (BIA)**- Participants will remove their shoes and socks to complete this assessment. They will be asked to stand on a BIA scale (Tanita) and hold two electrodes in either hand. The duration of this test is anticipated to take approximately 10 seconds per reading. Two readings will be taken and then averaged for measures of body weight (kg or lbs.), body fat percentage (%), and total body water (%). Subjects will be provided with a standard set of hospital scrubs to wear for body weight and composition measures.

**Dual-Energy X-Ray Absorptiometry (DEXA)**- A whole-body DEXA procedure will be used to assess bone mineral density, lean muscle weight (kg or lbs.), fat weight (kg or lbs.), and body fat percentage (%) at various body segments (e.g. total body, trunk, hip, leg). The subject will remove any metal or jewelry prior to the scan. They will be instructed to lie supine with their arms by their sides and asked to remain still while a scanning arm moves above them across the entire length of their body. One scan will be performed during **Visits 1 and 4**.

**Actiheart Continuous Heart Rate**- Continuous measurements of heart rate will be obtained using an Actiheart chest-strap monitor during **Visits 1 and 4** for all participants and for 3 randomly selected participants (1 per treatment group) in each cohort to monitor the intensity of exercise training sessions. The Actiheart is a wireless electronic measuring device that clips onto two electrodes placed approximately 1 to 2 inches below the left collarbone spaced apart at typical heart rate monitoring measurement sites.. An approximate 2 inch diameter circular area around each electrode site will be prepped using an alcohol swab, for measurement. The device electronically transmits measurements of heart rate to a software system. Subjects will

wear this device for the duration of **Visits 1 and 4**. Actiheart heart rate measurements will be taken once during week 2, week 4, and week 6 of exercise training for each of the 3 randomly selected participants (3 times total).

**Pulse Wave Velocity (PWV)**- Measurements of PWV (m/s) will be obtained from standard blood pressure and tonometry assessment using the ATCOR SphygmoCor device. This device is a non-invasive way to perform central blood pressure waveform assessment. During **Visits 2 and 2**, subjects will be asked to lie still in a supine position on a padded table surface for a duration of 10 minutes. A leg blood pressure cuff will be placed on the upper thigh. A technician will apply carotid tonometry simultaneously to inflating the blood pressure cuff to obtain blood pressure waveforms at the carotid and femoral artery sites. SphygmoCor software uses physical distance measurements between the sites to calculate velocity.

**Laser Doppler Blood Flow Heating Protocol**- Laser Doppler (Blood FlowMeter, Ad Instruments) will be used to assess cutaneous vascular conductance in response to a localized heating stimulus. Two small skin surface probes will be applied to the non-dominant forearm of the subject during **Visits 1 and 4**. Resting measurements will be obtained for 5 minutes followed by a measure of resting blood pressure. Localized skin heating will be accomplished with local heating units that will surround the skin surface probes of the laser Doppler. Both probes will be heated to a set temperature of 39°C (102°F) for 25 minutes. . The temperature of the probes will then be increased until a maximum temperature of 44°C (111°F) and held for 15 minutes . Blood pressure measurements will be obtained from the dominant arm every 10 minutes during the 40-minute heating protocol. From measures of blood pressure and the laser Doppler blood flow, cutaneous vascular conductance will be calculated as a ratio of skin blood flow to mean arterial pressure. Cutaneous vascular conductance will be expressed as a percentage of maximal conductance measured at the end of the heating protocol.

**Blood Pressure**- Blood pressure readings (mm Hg) of systolic and diastolic blood pressure will be taken using an automated sphygmomanometer on the dominant upper arm. During **Visits 1 and 4**, measurements will be taken during seated rest, every 10 minutes during the localized heating protocol, and every hour for 3-hours following ingestion of beetroot juice. During **Visits 2 and 3**, measurements will be taken during standing rest prior to the submaximal walking exercise, at minutes 3 and 5 during submaximal walking, and after 3 minutes of recovery following submaximal walking.

**Questionnaires**- A questionnaire will be given to participants in two parts (Part A and Part B) during **Visits 1 and 4**. The first part of the questionnaire consists of the Addenbrooke's Exam-III (ACE-III), which will be verbally administered by a trained member of our research team. This exam is designed to assess five cognitive domains including attention, memory, verbal fluency, language, and visuospatial abilities. Current mood states will be assessed using the Profile of Mood States (POMS) instrument. These questionnaires are also designed to obtain demographic, health, and physical activity habit information about our subjects.

**Venous Blood Draw-** A venous blood sample will be taken by trained personnel at the Indiana University Bloomington Student Health Center during **Visits 2 and 3**. Two 7mL, and one 4mL vials of blood will be taken at each timepoint for a total of 18mL x 2 visits = 36mL. The two 7mL vials of EDTA plasma samples will be centrifuged 1 x 10 minutes at 2500 x g at room temperature. Samples will then be aliquoted and stored at -80 degrees Celsius. Upon thawing, samples will be prepped wherein quantification of endothelial microparticles (sICAM-1, s-VCAM-1, sNCAM, MPO, IFNg, IL-1 $\beta$ , BDNF, TNF- $\alpha$ , and IL-10) will be performed. Flow cytometry will be used to obtain a complete blood count (CBC) using the 4mL vial of EDTA plasma sample.

**Nitric Oxide Breath Analysis-** The fraction of expired nitric oxide in exhaled breath will be assessed using a handheld digital breath analyzer (NIOX VERO). Subjects will be asked to exhale once into the analyzer prior to ingestion of beetroot juice and again 3-hours after ingestion to confirm a change in nitric oxide levels at **Visits 1 and 4**. During **weeks 3 and 6 of the supervised exercise training intervention**, random drop-ins will be conducted by a member of our research team to assess fractional exhaled nitric oxide levels to assess compliance with the beetroot supplementation by asking subjects to breathe once into the breath analyzer.

**Blood Oxygen Concentrations-** To monitor the concentrations of oxygen and methemoglobin in the blood both prior to and following acute beetroot juice ingestion, a fingertip pulse oximeter will be used (Masimo SpMet). Measurements of SpMet will be taken once every hour for 3-hours following ingestion of beetroot juice during **Visits 1 and 4**. A concentration of SpMet  $\geq$  12% indicates a serious adverse response to acute beetroot supplementation.

**Beetroot Juice Administration-** Participants randomized to receive exercise training and beetroot juice will be supplied with 140 mL of commercially-available beetroot juice (James White Drinks, UK) containing approximately 12 mmol of nitrate. Participants will be given a 4-week supply (24 bottles) which will then be repeated at the half-point of the exercise training progression. Participants will be instructed to consume the supplement between 2 to 3 hours prior to each exercise session to ensure training coincides with peak nitrate/nitrite bioavailability (14). Participant adherence will be determined at random, prior to exercise (on-site), during weeks 3 and 6 using a portable breath analyzer to monitor the fractional exhaled nitric oxide (NIOX MINO, NC) (17).

**Dietary Recall Assessment-** Participants will be asked to record all food, beverages, and supplements that they consumed within a 24hr period on six separate occasions using a paper handout supplied to them (see dietary recall handout in protocol attachments). They will be asked to record three times on one weekend and one weekday during the first week, and again during the last week of the 8Wk supervised exercise training sessions. They will be asked to complete the recalls within a 7-day period at both timepoints. Since this is not a primary outcome variable of interest, and will simply be used to describe amounts of dietary nitrate

consumed outside of the beetroot juice supplement, any subject who does not complete one or more of the recall entries will not be withdrawn from the remainder of study procedures. Subsequent analysis to obtain measures of food group equivalencies for nitrate containing food items (e.g. dark leafy greens) will be conducted using a validated Automated Self-Administered 24h (ASA24) dietary recall system. Approved study personnel will manually enter food, beverage, and supplement items into the electronic recall system to generate a report of dietary characteristics for each 24hr period.

**Isokinetic Dynamometry-** A Humac Norm System will be used to measure each subject's muscle contractile properties as previously described (18, 19) during **Visits 2 and 3**. Briefly, study participant will perform maximal knee extensions with their dominant leg at angular velocities of 0, 1.57, 3.14, 4.71, and 6.28 rad/s. (Not all older individuals may be able to achieve the highest velocity – if not, the highest achieved angular velocity and associated torque will be used in all subsequent calculations.) The subject will perform 3-4 knee extensions at each velocity, with 2 minutes of rest allowed between each set of contractions. To eliminate artifacts, data will be “windowed” to isolate the isokinetic phase and smoothed using a 9 point weighted moving average filter using Microsoft excel. The highest torque generated at each velocity will be used to calculate peak power at that velocity, after which the resulting power-velocity curve will be fit with a parabolic function to determine the subject's Pmax and Vmax (i.e., Y-maximum and 2nd Y-intercept of fitted parabola, respectively) as previously described (18, 19).

**Submaximal Walking Test-** During **Visits 2 and 3**, subjects will be outfitted with a flexible oronasal face mask (Korr CardioCoach) and chest-strap heart rate monitor. A metabolic cart will be used to obtain continuous breath-by-breath monitoring of oxygen consumption. Subjects will be asked to stand quietly on the treadmill belt for 3 minutes while resting measurements of heart rate and blood pressure are obtained. They will then walk at 2mph at a 0% grade for 6 minutes. Heart rate and blood pressure will be obtained at minutes 3 and 5 of walking. Following exercise, they will remain standing while rested for 3 additional minutes while heart rate is recorded each minute and blood pressure after the final minute. Subjects will be asked to rate their perception of effort during exercise at minutes 3 and 5 using a discrete visual analog scale (0-10).

**6-Minute Walk Test-** Consistent with standard procedures (20), participants will be instructed to walk for six minutes around an indoor, closed course during **Visits 2 and 3**. A chest-strap heart rate monitor will be worn to measure changes in heart rate before and after walking, and a triaxial accelerometer will be used to examine signal profile associated with movement complexity (i.e. movement accelerations) and estimates of energy expenditure (kilocalories). The accelerometer will be worn on the non-dominant hip and fastened with an elastic belt. Subjects will additionally be asked to identify their level of perceived exertion on a continuous visual analog scale (“no exertion” to “maximal exertion”) after the test.

**Supervised Exercise Training (CrossFit, Bloomington)-** Participants randomized to exercise training will perform combined aerobic and resistance workouts in a group setting with a cohort of approximately 4 women also enrolled in the study. There is a chance that participants will complete the exercise training sessions with other individuals who are not enrolled in the study. This will be outlined in the Informed Consent Statement provided to participants.

Full participation in the exercise training intervention is defined as attending 3 sessions per week for a total of 8 weeks (24 sessions total). The sessions will be supervised by a certified fitness professional who will make adjustments to the workouts based on individual needs/abilities. Each one-hour session will consist of a warm-up, instruction of the workout, a workout of combined aerobic and resistance training exercises, and cool-down. Intensity of the exercise sessions will be progressed gradually from weeks 1 to 8 and monitored by having participants identify their rating of perceived difficulty for each session using a discrete visual analog scale (0-10). The intensity of exercise sessions will also be monitored through continuous heart rate assessment (Actiheart) during week 2, week 4, and week 6 of training.

If participants miss (do not attend) a scheduled exercise training session, they will resume training at the next available scheduled session. The missed workout session will be recorded. Participants will be withdrawn from the study if they miss more than 3 consecutive exercise training sessions in any given week. Additionally, they must complete a minimum of 70% of the total 24 exercise training sessions (17 out of 24 sessions attended) to continue with follow-up assessments.

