## 1.0 Background & Rationale

Advancing age is a primary risk factor for cardiovascular disease (CVD), which remains a pervasive source of death and disability in modern society. Postmenopausal women, in particular, represent a segment of the population that exhibit greater rates of disability and CVD with advancing age compared to men (1). Based on data from the Women’s Health Initiative, wherein estrogen replacement therapy did not exhibit cardioprotective benefits (2), it is essential to consider alternative approaches that may possess therapeutic potential for attenuating CVD risk among postmenopausal women. Indeed, it has become increasingly clear that exercise training is vital to preservation and restoration of physiologic function to achieve optimal health/longevity in many populations (3). However, given that postmenopausal women do not characteristically possess the same responsiveness to exercise training compared to *pre*menopausal women (4) or men (5) – targeted efforts are needed to overcome the limitations of current exercise prescription. Such efforts may attenuate age-related shifts in arterial aging and cardiovascular disease risk by proving to be more effective at reducing vascular oxidative stress/inflammation, as well as, increasing gait/mobility and endothelial function in postmenopausal women.

CVD risk steepens during the menopausal transition (6), likely due to the combined effects of age-related oxidative stress (7), low-grade inflammation (8), and diminishing estrogen (9). Since nitric oxide is implicated in numerous physiological functions, including vasodilation and inhibition of platelet aggregation, boosting nitric oxide bioavailability represents an ideal target to restore physiologic function. From a mechanistic standpoint, age-related oxidative stress reduces nitric oxide bioavailability via the uncoupling of eNOS following the formation of peroxynitrate (10). Historically, the L-arginine-nitric oxide pathway was thought to be the primary source of endogenous nitric oxide production. More recently, though, the nitrate-nitrite-nitric oxide pathway has been identified wherein commensal bacteria on the dorsal surface of the tongue reduce ingested nitrate (e.g. beetroot juice) to nitrite (11). Swallowed nitrite can then be further reduced to stimulate nitric oxide-dependent signaling within the systemic circulation. Functionality of the nitrite-

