### 4.2 Exclusion Criteria

[figure not shown]
- Unable to provide informed consent
- < 18 years or > 75 years of age (confirmed by birth date listed on participant's driver license at screening visit)
- Body mass index < 25.0 or >39.9 kg/m^2 (measured on-site at screening visit)
- Greater than stage II hypertension (i.e. >159/99 mm Hg)
- Current smoker (self-report)
- Currently pregnant, lactating, or trying to become pregnant (self-report)
- Habitually exercise training  $\geq$  3 times per week (self-report)
- Significant orthopedic limitations or other contraindications to strenuous exercise
- Live or work >50 miles from Bloomington study site or do not have transportation to the study site
- Anticipate elective surgery during the study period
- Plan to move residence or travel out of the local area during the study period
- Current use of anti-coagulants (e.g. Coumadin or Warfarin)
- Current use of prescription medications that affect heart rate or blood vessel dilation (e.g. phosphodiesterase-5 inhibitors, proton pump inhibitors, systemic  $\beta$ -adrenergic blockers, nitrates, calcium channel blockers, hormone replacement therapy) (self-report and confirmed on-site at screening visit)
- Psychological or social characteristic that would interfere with their ability to fully participate in the study (i.e. taking longer than allowed time to complete cognitive assessments)

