Based on participant responses to the questions, research personnel will determine preliminary eligibility for an on-site visit. If it appears the participant meets the preliminary eligibility, an on-site visit will be scheduled, and a consent form will be mailed / emailed to the participant for their consideration and review. After the study participant has had several days to review the consent form, research personnel will call the participant to answer any further questions regarding the consent form. Participants will be enrolled in small ( $n = 9$ ) cohorts or "waves" to facilitate social support and adherence to the supervised exercise training sessions. We anticipate having 9 waves to successfully reach our target  $n$ . This assumes that each wave will have 4 participants, hence, 4 participants x 9 waves = 36 total participants.

At the on-site screening visit, research personnel will once again cover inclusion/exclusion criteria, study procedures, requirements, and risks. Following written informed consent, participants will have their body weight and standing height measured to determine their body mass index (i.e., 25.0-39.9 kg/m^2). Current prescription drug use will be recorded by having

participants physically bring their prescription labels or medication bottles to the testing site. Additionally, participants will complete a Medical History Questionnaire (see attachments).

Written authorization will be obtained from consented participants to allow research personnel to contact the participant's primary care physician to receive physician's clearance prior to study testing visits. The physician will be asked to provide their assent or dissent for their patient to participate in the exercise testing protocols and supervised group exercise sessions involved with this study. They will have the option to indicate any modifications that may be necessary for the patient to participate safely. The Physician Clearance Form (see attachments) will be faxed to the patient's physician following the screening visit.

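### The protocol's one described route for juice nitrate runs through tongue bacteria, yet the text shown neither addresses antibacterial mouthwash nor records mouthwash or antibiotics after screening

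*Combined protocol and SAP*

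**What the plan says.** **Mechanism.** Section 1.0 (Background & Rationale) states that "commensal bacteria on the dorsal surface of the tongue reduce ingested nitrate (e.g. beetroot juice) to nitrite", and then: "Swallowed nitrite can then be further reduced to stimulate nitric oxide-dependent signaling within the systemic circulation". It describes no other route for the juice.

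**Instruction.** Section 7.0 (Beetroot Juice Administration) fixes the volume and the timing: "Participants will be instructed to consume the supplement between 2 to 3 hours prior to each exercise session". Section 8.0 also gives timing only.

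**Eligibility and drug recording.** Section 4.2 excludes "Current use of prescription medications that affect heart rate or blood vessel dilation", and anti-coagulants separately. The readable list names neither antibiotics nor mouthwash. Section 6.0 says "Current prescription drug use will be recorded by having" women bring labels or bottles to the screening visit, and Section 8.0 repeats that check. The calendar has no later medication row.

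**Recording during training.** Women are asked to "record all food, beverages, and supplements that they consumed within a 24hr period on six separate occasions", in the first and last weeks of training.

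**Breath tests.** At Visits 1 and 4 every woman gives an exhaled nitric oxide reading before the juice and "again 3-hours after ingestion to confirm a change in nitric oxide levels". During training, "Participant adherence will be determined at random, prior to exercise (on-site), during weeks 3 and 6 using a portable breath analyzer". No cut-off, action or analysis rule is attached to a low reading.

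**The concern.** The protocol takes care over other determinants of nitrate exposure: the dosing window, background dietary nitrate, and a washout of at least 7 days after the Visit 1 dose. The bacterial step in its own rationale gets no comparable attention.

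If a woman suppresses those bacteria, she can be fully compliant with the juice and still receive less of the exposure under study. Two things are at stake. First, the BR+EX versus EX effect sizes in Aims 2 and 3, which Section 12.0 names as input to a larger investigation, would be pulled toward zero. Second, the drop-in breath reading is meant to measure adherence. If exhaled nitric oxide depends on the same oral step, a woman who drank but did not convert would look like one who did not drink. Use that is not recorded at the time is hard to reconstruct later.

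**Working it through.** **1. Where use could be captured in the text shown**

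| Source | Prescribed antibiotic | Antibacterial mouthwash |
|---|---|---|
| Section 4.2 exclusions | not listed | not listed |
| Screening medication check (6.0, 8.0) | yes, if in use then | only if prescribed |
| Juice instructions (7.0, 8.0) | no | no |
| 24-hour recalls (7.0) | no | no |
| Weeks 3 and 6 drop-ins (7.0) | breath reading only | breath reading only |
| Study calendar after screening (8.0) | no row | no row |

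The gap is therefore non-prescribed mouthwash throughout, and any antibiotic started after screening.

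**2. Inputs for an illustration**

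The plan gives no share of users, degree of suppression or sample-size calculation, so it has no figure of its own to reproduce.
- Effect size: Section 2.2 anticipates small to medium. Section 12.0 sets these at d = 0.2 and 0.5. I use 0.50.
- Women per arm: 20 completers / 2 = 10 and 24 randomized / 2 = 12 (Section 3.1); 4 × 9 = 36, and 36 / 2 = 18 (Section 6.0).
- Share of BR+EX women fully blocked, f: 10% to 40%. This is my assumption.

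**3. Dilution**

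If a share f of BR+EX gets no juice effect and the rest get d (in SD units), the mean difference is (1 − f)d. The BR+EX variance becomes 1 + f(1 − f)d². Pooling with an EX variance of 1 gives

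observed d = (1 − f)d / √(1 + f(1 − f)d²/2).

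- f = 0.10: 0.45 / √1.01125 = 0.447
- f = 0.25: 0.375 / √1.02344 = 0.371
- f = 0.40: 0.30 / √1.03 = 0.296

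The shift is 0.50 − 0.447 = 0.05 at the low end and 0.50 − 0.296 = 0.20 at the high end.

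**4. Sampling error, for scale**

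The approximate 95% half-width for d is 1.96 × √(2/n + d²/(4n)), with n per arm and d = 0.50.

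- n = 10: 1.96 × √0.20625 = 0.89
- n = 12: 1.96 × √0.17188 = 0.81
- n = 18: 1.96 × √0.11458 = 0.66

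The illustrated shift is smaller than the sampling error throughout. Sampling error falls on either side of the truth and shrinks with more women. Dilution does neither.

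**5. What the breath readings can tell**

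At Visits 1 and 4 the dose is known to have been taken at the visit, so a flat response points to non-response rather than a missed dose, although its cause stays unknown. At weeks 3 and 6 the dose is taken beforehand. A low reading then has at least two explanations, not drinking and not converting, and nothing else recorded distinguishes them.

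**The case against.** Several points on the other side stand.

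- **A reader might infer that the protocol says the juice works only through tongue bacteria.** It does not. Section 1.0 describes that route without ruling out others.
- **A reader might infer that antibiotics are never recorded, or that mouthwash is certainly never captured.** Neither can be established. A prescribed antibiotic in use at screening would be recorded. Questionnaire A+B, given at Visits 1 and 4 and covering health information, is an attachment not shown, as are the Medical History Questionnaire and the Participant Instruction Sheet. A figure at the head of Section 4.2 is also missing from the text shown.
- **Non-response is partly measured already.** If exhaled nitric oxide reflects oral conversion, the paired tests may flag women who do not respond, at Visit 1 before randomization. It would be wrong to say that analysts could do nothing. The tests do not cover the 8 weeks, and no rule says how they are used.
- **A reader might turn the dilution into a sample-size penalty.** From step 3, (0.50/d observed)² is 1.01125/0.81 = 1.25 to 1.03/0.36 = 2.86. The documents do not support that as a finding. It needs complete blocking for the whole intervention in a share that I assumed, and a larger trial that controls use. If the larger trial enrolled similar women without restriction, the effect under usual habits would be the right planning input. Even then, recorded use would be needed to know which effect had been estimated.
- **The primary aim is feasibility, and Section 12.0 disclaims confirming efficacy.** This limits the reach of the point to the secondary and tertiary aims and the juice-adherence check.

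**Conclusion.** The point holds in a limited form. The described mechanism depends on oral bacteria. The text shown gives no mouthwash instruction, and it records neither mouthwash nor antibiotics after screening. Under-exposure in a fully compliant woman is therefore possible and, outside the paired breath tests, largely invisible.

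The direction is toward zero for Aims 2 and 3. The size is unknown: a true d of 0.50 seen as about 0.45 to 0.30 rests wholly on the assumed 10% to 40% of women fully blocked. Partial or occasional suppression would give less. The completion criterion of 20 of 24 does not depend on this. It is a cheap improvement, not a flaw that undermines the trial, and it shrinks if the unseen attachments already cover it.

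**What to change.** 1. In Section 7.0 (Beetroot Juice Administration), ask women in both arms to avoid non-prescribed antibacterial mouthwash from Visit 1 to Visit 4, with no change to any prescribed product. Asking both arms keeps the request from becoming a difference between them. It also covers the test dose that all women take at Visits 1 and 4.
2. Record mouthwash and antibiotic use at Visits 1 to 4 and at the week 3 and 6 drop-ins, and add a calendar row. If Questionnaire A+B or the Participant Instruction Sheet already carries this, cite it in the protocol and add only the missing contacts.
3. State that low exhaled nitric oxide readings will be read alongside recorded use before a woman is described as non-adherent.
4. In Section 12.0, keep the comparison of all randomized women as the main estimate and report use by arm. Treat any estimate that leaves out users as descriptive only: it selects on behavior after randomization and would be very imprecise at about 10 to 18 per arm.

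The cost is one instruction line and one or two form questions. The downside is a small burden on participants and a slightly more selected setting. If the sponsor prefers not to restrict mouthwash, recording alone still makes low readings easier to interpret.
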